Criteria for Evaluation	
Descriptive assessments of long-term efficacy and safety will be made between the parent study Baseline and the end of the extension study (Week 52) for the following parent study treatment groups:
 
 
Parent Study Group A: Randomized to 24 weeks of oral relugolix 40 mg once daily co-administered with 1.0 mg estradiol and 0.5 mg norethindrone acetate in the parent study;
 
Parent Study Group B: Randomized to 12 weeks of oral relugolix 40 mg once daily followed by 12 weeks of oral relugolix 40 mg once daily co-administered with 1.0 mg estradiol and 0.5 mg norethindrone acetate in the parent study;
 
Parent Study Group C: Randomized to placebo in the parent study.
 
 
The parent study Baseline will be used as the reference point for this extension study for all change from baseline-related endpoints. The pain scores during the Baseline Pain Assessment Period of the parent study will establish the patient's baseline for both the parent study and the extension study.
 
Primary Efficacy Endpoints
 
 
Proportion of women who respond or maintain response at Week 52/Early Termination, based on their dysmenorrhea NRS scores;
 
Proportion of women who respond or maintain response at Week 52/Early Termination, based on their NMPP NRS scores.
 

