## 1.1. Schedule of Activities

**Table 1-1 Schedule of Activities for Study MVT-601-3103**

PERIOD	OPEN-LABEL TREATMENT									SAFETY FOLLOW-UP
	Week 24/Baseline (Week 24 of Parent Study; Baseline of Extension Study)	Week 28	Week 32	Week 36	Week 40	Week 44	Week 48	Week 52 a (or Early Termination of Study Drug)	Un-scheduled b	Follow-Up c (~30 days after last dose of study drug)
Visit Window (days)	Parent Study Day 169 -10/+20	±7	±7	±7	±7	±7	±7	±7	-	-3 to +18
Informed Consent	X d									
Review Eligibility Criteria	X									
Concomitant Medications e	X f	X	X	X	X	X	X	X	X	X
Vital Signs (BP, HR, Temperature)	X g	X	X	X	X	X	X	X	X h	X
Weight	X g			X				X	X h	
Complete Physical Exam	X g							X	X h	
Visual Acuity i	X g									
Signs and Symptoms-Directed Physical Exam j		X	X	X	X	X	X		X h	X
12-Lead ECG k	X g							X	X h	
Clinical Laboratory Tests l	X g,m	X	X	X	X	X	X	X m	X h	X
Pharmacodynamics Sample n	X g,m							X m	X h,m	
Urinalysis	X g							X	X h	
Pregnancy Test (Urine)	X g	X	X	X	X	X	X	X	X h	X

PERIOD	OPEN-LABEL TREATMENT									SAFETY FOLLOW-UP
	Week 24/Baseline (Week 24 of Parent Study; Baseline of Extension Study)	Week 28	Week 32	Week 36	Week 40	Week 44	Week 48	Week 52 a (or Early Termination of Study Drug)	Un-scheduled b	Follow-Up c (~30 days after last dose of study drug)
Visit Window (days)	Parent Study Day 169 -10/+20	±7	±7	±7	±7	±7	±7	±7	-	-3 to +18
Daily eDiary o	X g	X	X	X	X	X	X	X		X
Site Review of eDiary Data	X g	X	X	X	X	X	X	X	X h	X
Bone Densitometry p	X g			X				X q,r	X h	
Endometrial Biopsy	X g,s								X h	
Dispense Study Treatment	X	X	X	X	X	X	X		X h	
Dispense or prescribe protocol-specified analgesic drugs t	X	X	X	X	X	X	X	X	X h	
Treatment Compliance		X	X	X	X	X	X	X	X h	
Take Study Drug Dose in Clinic	X u							X	X h	
Daily Self-Administration of Study Treatment v		X								
Take Protocol-specified Rescue Analgesics as Needed w		X								

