Patients will have received their last dose of study drug in the parent study on the day prior to the Week 24/Baseline visit, and will receive their first dose of study drug for this extension study in the clinic after the patient is determined to be eligible for this extension study and has provided informed consent to participate. Therefore, results of testing required for eligibility must be available on or prior to the Week 24/Baseline visit. The administration of the first dose of study drug for MVT-601-3103 will define enrollment into this study. Study participants will then take the open-label study treatment (relugolix 40 mg co-administered with estradiol 1.0 mg and norethindrone acetate 0.5 mg) orally once daily for 28 weeks.

During the 28-week Open-Label Treatment Period and the ~30-day Follow-Up Period, patients will continue to record study treatment, assessment of pain using the NRS, menstrual bleeding, analgesic use, and the functional effects of endometriosis-associated pain (sB&B) in the electronic diary (eDiary). Only study-specific rescue analgesic medications should be used starting with the Week 24/Baseline visit and through the Follow-Up visit and these medications will be taken for control of pain and not prophylactically. Health-related quality of life questionnaires; PGIC for dysmenorrhea, NMPP, and dyspareunia; and PGA for pain and function will be completed during the visits on an electronic tablet or on paper, according to the Schedule of Activities ([Section 1.1](#)).

At the Week 36 visit and Week 52/Early Termination visit, each patient will have an assessment of bone mineral density via DXA.

[figure not shown]
Safety will be assessed throughout the study by the monitoring of adverse events, vital signs and weight, physical examinations, clinical laboratory tests, 12-lead ECGs, and bone mineral density with DXA.

Patients with a bone mineral density loss of  $> 3\%$  at the lumbar spine (L1-L4) or total hip at their Week 52/Early Termination visit (or most recent scan, if the Week 52/ET scan was not done) relative to the parent study Baseline measurement will undergo another bone densitometry scan at  $6 (\pm 1)$  months after the last dose of study medication.

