### **6.2. Open-Label Treatment Period (Week 24/Baseline to Week 52)**

As denoted in the Schedule of Activities (see [Section 1.1](#)), certain Week 24 visit procedures of MVT-601-3101 or MVT-601-3102 will serve as the Week 24/Baseline procedures for patients

who are interested in participating in this extension study, and these Week 24 procedures will be performed under the informed consent for the parent study.

Patients will be required to sign an informed consent form for the extension study, and will be eligible if they meet all of the eligibility criteria.

Once eligibility is determined, all additional Week 24/Baseline visit procedures described in the Schedule of Activities (see [Section 1.1](#)) that were not performed as part of the Week 24 visit of the parent study will be completed. These include the following:

- Informed consent (unless signed previously);
- Record concomitant medications;
- Update the patient's status in the IVRS/IWRS as being in the MVT-601-3103 and receive the lot numbers for study drug allocation;
- Dispense study treatment;
- Dispense or prescribe protocol-specified analgesic drugs;
- Transition the patient within her eDiary from the parent study to MVT-601-3103
- Take study drug dose in clinic; and
- Record adverse events, if any.

The Week 24 visit date in the parent study is defined as the date that the last procedures for the Week 24 visit were completed, acknowledging that the Week 24 visit procedures may be completed on different dates. Patients will have received their last dose of study drug in the parent study on the day prior to the Week 24/Baseline visit, and will receive their first dose of study drug for this extension study in the clinic after the patient is determined to be eligible for this extension study and has provided informed consent to participate. Therefore, results of testing required for eligibility must be available on or prior to the Week 24/Baseline visit.

Patients will continue recording data in their eDiary daily and taking protocol-specified analgesics as needed. Following the Week 24/Baseline visit, on-treatment study visits will occur at Weeks 28, 32, 36, 40, 44, 48, and 52. Sites will monitor diary completion using the TrialManager web portal throughout the study.

Accountability for study drug will be performed at each visit. Instructions for analgesic medication usage will be reinforced at each visit.

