### **9.4. Efficacy Analyses**

Unless otherwise specified, efficacy analyses will be conducted using the mITT Population.

Efficacy endpoints will be summarized by the original treatment groups assigned in the parent study.

The point estimates and 2-sided 95% confidence intervals (CI) for the primary efficacy endpoints (proportion of responders based on dysmenorrhea NRS scores and use of rescue analgesic medications, proportion of responders based on NMPP scores and use of rescue analgesic medications) will be calculated.

A responder at a given time point and for a specific type of pain (dysmenorrhea or NMPP) is defined as a patient who had a reduction in that type of pain from Baseline greater than or equal to a pre-determined threshold and who did not have an increase in the use of rescue analgesic medications for endometriosis-associated pain compared with the use at Baseline. Patients who had a pain reduction less than the pre-determined threshold or who had an increase in the use of analgesics for endometriosis-associated pain will be considered non-responders. The pain reduction thresholds will be determined for NMPP and dysmenorrhea separately (see the SAP for details) for the parent studies and these same thresholds will be applied to this study.

Baseline values are calculated using the Baseline pain assessment period, which is defined as the period from the date of the first dose of placebo in the parent study Run-In Period through the day prior to the first dose of randomized study drug. Patients' average NRS pain scores and use

of rescue analgesic medications for endometriosis-associated pain (dysmenorrhea or NMPP) will be compared between a given visit-specific pain assessment period (eg, Week 28, Week 32, etc.) and the Baseline pain assessment period. The visit-specific pain assessment period is defined as the last 35 calendar days immediately prior to and including the last dose of study drug treatment received prior to the visit date.

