For any pain assessment period (Baseline or visit-specific), the average NRS scores will be calculated for dysmenorrhea and NMPP separately. An average NRS score for dysmenorrhea is calculated as the average NRS score over the days with menses during a given pain assessment period. An average NRS score for NMPP is calculated as the average NRS score over the days without menses during a given pain assessment period. The analgesic use for a given pain assessment period is summarized by total dose count defined as the average daily dose count taken during the given pain assessment period multiplied by 35. Additional details on calculating dose counts and on the precise definition of an increase in analgesic use will be provided in the SAP.

Descriptive statistics will be provided for efficacy endpoints (listed below) similar to those used for the parent studies.

- Change from the parent study Baseline to Week 52 in the EHP-30 Pain Domain scores;
- Change from the parent study Baseline to Week 52/EOT in the mean dysmenorrhea NRS score;
- Proportion of patients who are better or much better on the PGIC for dysmenorrhea at Week 52/EOT;
- Change from the parent study Baseline to Week 52/EOT in the mean NMPP NRS score;
- Proportion of patients who are better or much better on the PGIC for NMPP at Week 52/EOT;
- Change from the parent study Baseline to Week 52/EOT in the mean dyspareunia NRS scores;
- Proportion of patients who are better or much better on the PGIC for dyspareunia at Week 52/EOT;
- Change from the parent study Baseline to Week 52/EOT in the mean dyspareunia functional impairment on the sB&B scale;
- Change from the parent study Baseline to Week 52/EOT in severity scores on the PGA for pain;
- Proportion of responders at Week 52/EOT based on EHP-30 Pain Domain scores;
- Change from the parent study Baseline to Week 52/EOT in function impairment on the PGA for function;
- Change from the parent study Baseline to Week 52/EOT in each of the non-pain EHP-30 domains (Control and Powerlessness, Social Support, Emotional Well-Being, and Self-Image);
- Change from the parent study Baseline pain assessment period to Week 52/EOT in dysmenorrhea-related functional effects (sB&B);
- Change from the parent study Baseline pain assessment period to Week 52/EOT in NMPP-related functional effects (sB&B).

For binary endpoints, the point estimate and 2-sided 95% CI for the proportion will be provided by parent study treatment group.

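### The 35-day pain window has no stop at the first extension dose, so former placebo patients (Group C) carry placebo days into Week 28 and into early Early Termination results

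*Protocol*

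**What the plan says.** Section 9.4 compares average NRS scores and rescue analgesic use in a visit-specific period with the parent-study Baseline period. It defines the visit-specific period as "the last 35 calendar days immediately prior to and including the last dose of study drug treatment received prior to the visit date" and gives Week 28 and Week 32 as examples. No earliest start is set. The original protocol and Amendment 1 use the same wording.

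Three features of the design bear on this rule:

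- **Rollover has no gap.** Section 4.1 says "Patients will have received their last dose of study drug in the parent study on the day prior to the Week 24/Baseline visit", and that at this visit they "will receive their first dose of study drug for this extension study in the clinic after the patient is determined to be eligible". Table 1-1 places the visit at "Parent Study Day 169 -10/+20". Under Section 6.2, "on-treatment study visits will occur at Weeks 28, 32, 36, 40, 44, 48, and 52", each with a window of ±7 days in Table 1-1.
- **The endpoints include early stoppers.** The first primary endpoint in the Synopsis is "Proportion of women who respond or maintain response at Week 52/Early Termination, based on their dysmenorrhea NRS scores". The second is the same for nonmenstrual pelvic pain (NMPP). The secondary changes in mean dysmenorrhea and NMPP scores are read at Week 52 or end of treatment.
- **The score depends on which days fall in the window.** "An average NRS score for dysmenorrhea is calculated as the average NRS score over the days with menses during a given pain assessment period". NMPP uses the days without menses. Analgesic use is the average daily dose count over the same period, multiplied by 35.

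Results are summarized by parent-study group, and Group C took placebo until rollover.

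**The concern.** The window is longer than the nominal interval between the switch and the first extension visit. In Group C, a result presented as an extension-treatment result at Week 28 therefore contains days on placebo. The same happens at Early Termination for anyone who stops soon after rollover, and that time point feeds the primary responder endpoints.

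Both parts of the responder definition are exposed, because pain reduction and analgesic use share the period. NMPP and analgesic use are diluted roughly in proportion to the placebo days. Dysmenorrhea can be affected more strongly, because only menses days count. If bleeding stops after the switch, the only menses days left in the window may be those from the placebo phase.

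**Working it through.** **Inputs.** Window length is 35 days, ending on the last dose before the visit date (Section 9.4). The first extension dose is on the day of the Week 24/Baseline visit, and the last parent-study dose is the day before (Section 4.1). Visit days come from Table 1-1. Daily dosing without missed days is assumed.

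**The plan's own figure.** Week 24 is 24 × 7 + 1 = Day 169, as Table 1-1 states.

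**Formula.** Let D be the day of the first extension dose and V the visit day. The window ends on day V − 1 and holds V − D extension days, so

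placebo days in Group C = max(0, 35 − (V − D)).

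**Week 28, nominal.** D = 169 and V = 28 × 7 + 1 = 197. Extension days are 28 and placebo days 35 − 28 = 7, or 7/35 = 20%. The window is Days 162 to 196, of which Days 162 to 168 are placebo.

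**Week 28, visit timed from rollover ±7 days.**

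- 7 days early: 21 extension days and 14 placebo days (40%).
- 7 days late: 35 extension days and no placebo days.

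**Visits timed from parent Day 1 (an assumed reading).** The schedule header in the original protocol points this way, but the header in Amendment 1, as it appears here, does not repeat it. With the latest permitted rollover, D = 169 + 20 = 189:

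- Week 28 (Days 190 to 204): 1 to 15 extension days, so 34 to 20 placebo days.
- Week 32 (Days 218 to 232): 29 to 43 extension days, so 6 to 0 placebo days.

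**Early Termination after k extension doses.** Placebo days = 35 − k:

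| k | Placebo days | Share of window |
|---|---|---|
| 7 | 28 | 80% |
| 14 | 21 | 60% |
| 21 | 14 | 40% |
| 28 | 7 | 20% |
| 35 or more | 0 | 0% |

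**Week 52.** The smallest extension count over the permitted windows is (365 − 7) − 189 = 169 days, so there is no overlap.

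**Groups A and B.** Group B took relugolix with add-back for its last 12 parent-study weeks (84 days), and Group A throughout. A window that includes any extension day reaches back at most 34 days before rollover, so for these groups the regimen is the same on both sides.

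**What dilution does to an NMPP score (illustration).** Assume a reduction of 4 points on extension treatment and 2 on placebo, with placebo share w. The scored reduction is 4(1 − w) + 2w, giving 3.6, 3.2, 2.8 and 2.4 points for w = 20%, 40%, 60% and 80%. The responder thresholds are not in the protocol, so this does not translate into a change of responder status.

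**Bound on the primary proportion.** If a share s of the analysed Group C patients stop with fewer than 35 extension doses, changing the window can move the proportion by at most s. For assumed s of 2%, 5% or 10%, that is at most 2, 5 or 10 percentage points, reached only if every such woman changed status in the same direction.

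**The case against.** The strongest case against is that this hardly matters for what the trial reports. No listed endpoint is read at Week 28, women who reach Week 52 have no overlap, and the analyses are descriptive with no between-group comparison. All of that stands, and it limits the weight of the point. It does not remove the Early Termination route into the primary endpoints.

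A second objection is that Section 9.4 leaves derivations and missing data to the SAP. That would answer a gap, but here the protocol states a complete rule that gives a mixed-treatment score for women who switch. An SAP that cut the window at rollover would depart from that text.

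Third, the text is from Amendment 1. Amendments 2, 3 and 3.1 exist, treatment is later extended to Week 104, and their Section 9.4 is not in the part of the document at hand. Whether the rule survived cannot be checked.

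Fourth, the modified intent-to-treat population in Section 9.2 includes parent-study patients who never enter the extension. Repairing the window would therefore not make the Group C primary proportion a pure extension-treatment result. That also stands.

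A reader might go further and infer that most Week 28 windows are heavily contaminated. Counting every permitted pair of rollover and Week 28 days equally, timed from parent Day 1, about 86% of pairs contain placebo days, with a mean of 12.5. Those figures describe the permitted grid under an assumed timing. The documents say nothing about how visits are actually distributed, so they do not forecast what patients will have.

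**Conclusion.** The point holds for Group C. As written, the rule puts 7 of 35 placebo days in the nominal Week 28 window (0 to 14 with visits within 7 days of their nominal distance from rollover). It puts 35 − k placebo days in the Early Termination window of a woman with k < 35 extension doses. The dysmenorrhea score in such a window could rest anywhere from not at all to entirely on placebo-phase days, depending on when bleeding occurred.

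It would be tempting to conclude that the Group C primary estimate is materially depressed. The documents do not support that, because they give no number of early stoppers and the SAP may handle these women separately. The effect is unquantified and probably small. Its likely direction is an understated Group C response, on the assumption that response on placebo is lower.

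The correction is worth making because it is cheap and removes an avoidable ambiguity. It does not threaten the Week 52 results of women who complete treatment.

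**What to change.** State in Section 9.4, and mirror in the SAP, that an extension pain assessment period starts no earlier than the first dose of extension study drug. Its length is then the shorter of 35 days and the days from that dose through the last dose before the visit. Analgesic use can still be scaled as average daily count × 35, which already accommodates a shorter period.

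State also that a shortened window with no on-treatment menses days is handled by the same no-menses or missing-data rule as any other post-baseline window, and is not filled from parent-study placebo days. That settles how such a woman counts in the primary proportion.

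The cost is a short text change and some programming, with no new data. Windows with 35 or more extension days are unchanged. The downside is fewer diary days early on: 28 at the nominal Week 28 visit, 21 if it is 7 days early, and only 7 for a woman who stops after 7 doses. For very early stoppers, a diluted dysmenorrhea score may become a missing one.

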## 9.5. Safety Analyses

Safety assessments will include treatment-emergent adverse events, vital signs and weight, physical examinations, clinical laboratory tests, 12-lead ECG, and bone mineral density with DXA. Safety summaries by treatment group will be performed using treatment groups defined based on the actual randomized treatment received in the parent study.

The treatment-emergent period will be defined as the period of time from the first dose date and time of randomized study drug in the parent study through 30 days after the last dose of study drug, or the date of initiation of another investigational agent or hormonal therapy affecting the hypothalamic-pituitary-gonadal axis or surgical intervention for endometriosis, whichever occurs first. Safety will be assessed through summaries of adverse events, the frequency of treatment discontinuations due to adverse events, laboratory evaluations, and bone densitometry results.

The severity of all adverse events is to be evaluated by the investigator based on the National Cancer Institute CTCAE. All adverse events will be coded to preferred term, high level term, and system organ class using MedDRA 20.0 or higher. The incidence of adverse events will be presented by MedDRA system organ class and preferred term, relationship to study drug treatment, and severity. A patient reporting the same adverse event more than once is counted once, and at the maximum severity or strongest relationship to study drug treatment when calculating incidence.

Laboratory data consist of chemistry, hematology, and hormonal tests. Only data collected by the central laboratory will be used to do the analyses. The National Cancer Institute CTCAE will be used to categorize toxicity grade for the laboratory parameters. Shift tables will be provided for each gradable parameter to summarize baseline toxicity grade versus post-baseline toxicity grade. For laboratory parameters that are not gradable by the CTCAE, a shift table based upon the normal range (low, normal, and high) will be provided for each parameter to summarize the parent study Baseline versus post-baseline results. All data will be listed and summarized by visit. The change from parent study Baseline to each post-baseline study visit will be presented by parent study treatment group for each laboratory test.

For vital signs parameters, including temperature, all data will be listed and summarized by visit. The change from parent study Baseline to each post-baseline study visit will be presented by parent study treatment group for each parameter.

Clinical laboratory data consist of chemistry, hematology, and hormonal tests. Only data collected by the central laboratory will be used to do the analyses. ECGs will also be read centrally. The distributions of QTc interval will be summarized at each visit. All data will be listed and summarized by visit. The change from parent study Baseline to each post-baseline study visit will be presented by treatment group for each ECG parameter.

The incidence of vasomotor symptoms as assessed through adverse event reporting will be summarized by the parent study treatment arm.

Bone mineral density data will be collected and analyzed by the central radiology laboratory including bone mineral content (g), bone area (area, cm^2), and bone mineral density (g/cm^2) each for L1, L2, L3, L4, total hip, and femoral neck, and average bone mineral density of L1-L4 (lumbar spine), Z-score for bone mineral density lumbar spine (L1-L4), total hip, and femoral neck.

For the relugolix add-back treatment Group A, the lower bound of the 95% CI for (arithmetic) mean percentage change at Week 52 from parent study Baseline in bone mineral density lumbar spine (L1-L4) will be compared with a pre-specified clinically acceptable threshold of -2.2% to evaluate magnitude of bone mineral density loss after 52 weeks of treatment. If the lower bound is > -2.2%, the bone mineral density loss for the relugolix add-back treatment will be considered insignificant. As supportive analysis, least square means and 95% CI for percent change at Week 52 from parent study Baseline in bone mineral density will be provided based on mixed effects model (assumed missing at random) for each parent study treatment group.

All data will be listed and summarized by visit. The absolute change and percent change from parent study Baseline to Weeks 36 and 52 and associated 95% CIs will be presented by the parent study treatment group for each bone mineral density parameter. The number and percentage of patients meeting a bone mineral density decline of at least 4%, 5%, 6%, or 7% by body area (lumbar spine, total hip, or femoral neck) will be estimated with 95% CIs by the parent study treatment group.

Additional analyses will be performed to examine the correlation between bone mineral density loss with demographic and baseline characteristics and with treatment exposure. Details will be provided in the SAP.

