#### **4.6. Contraception/Pregnancy Avoidance**

In this study, medications and devices containing hormones for contraception are excluded, and patients must agree to use nonhormonal contraception throughout the study including through 30 days following the last dose of study drug, unless any of the following apply:

- Has a sexual partner(s) who was vasectomized at least 6 months prior to the Week 24/Baseline visit;
- Had a bilateral tubal occlusion (including ligation and blockage methods such as Essure™) at least 6 months prior to the Week 24/Baseline visit (patients with Essure must have prior confirmation of tubal occlusion by hysterosalpingogram) and there must be no evidence of post-Essure syndrome;
- Has a nonhormonal intrauterine device (eg, Paragard®) placed in the uterus;
- Is not sexually active with men; periodic sexual relationship(s) with men requires the use of nonhormonal contraception as described below;
- Practices total abstinence from sexual intercourse, as her preferred lifestyle; periodic abstinence is not acceptable.

The only acceptable methods of contraception for those for whom one of the above methods do not apply are:

- Condom (male or female condom) with or without spermicide (cream, spray, foam, gel, suppository, or polymer film);
- Diaphragm with spermicide (condom may or may not be used);
- Cervical cap with spermicide (condom may or may not be used); or
- Vaginal sponge impregnated with spermicide used with a condom.

Patients will be provided with information on acceptable methods of contraception as part of the informed consent process and will confirm with signing of the consent form that they understand the requirements for avoidance of pregnancy during the course of the study. Patients may not donate ova during the course of the study and for 2 months following the last dose of study drug.

A patient may start hormonal contraception 4 weeks after her last study dose of study drug provided her menstrual cycle has returned.

Urine pregnancy tests will be performed at monthly intervals during the study (including just prior to receiving the first dose of study drug), and patients will receive continued guidance with respect to the avoidance of pregnancy as part of the study procedures. Patients who become pregnant during the study will be withdrawn from the study and followed for pregnancy outcome (see [Section 7.8](#)).

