### **5.10.3. Prohibited Non-Drug Therapies**

Surgical treatment of endometriosis is prohibited from the Week 24/Baseline visit until the patient's final study visit unless urgently needed for patient safety.

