### 7.2.1. Adverse Event Reporting Period

Adverse events and serious adverse events will be collected under this extension study protocol from the administration of the first dose of extension study drug until the Follow-up visit approximately 30 days after the last dose of study drug or the date of initiation of another

investigational agent or hormonal therapy affecting the hypothalamic-pituitary-gonadal axis or surgical intervention for endometriosis, whichever occurs first, as also specified in the study Schedule of Activities ([Section 1.1](#)). Serious adverse events reported to the investigator after the safety reporting period should be reported to the sponsor if the investigator assesses the event as related to the study drug treatment.

Reporting instructions for serious adverse events are provided in [Section 7.6](#).

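### The treatment-emergent period in Section 9.5 ends at a new hormonal, surgical or investigational treatment even while study drug continues, and the matching collection cut-off in Section 7.2.1 conflicts with the visit schedule

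*Protocol*

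**What the plan says.** All references are to Protocol Amendment 1. The original protocol has the same cut-offs in its Sections 7.2.1 and 9.5.

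- **Section 9.5, treatment-emergent period.** It runs from the "first dose date and time of randomized study drug in the parent study through 30 days after the last dose of study drug". It ends sooner if another investigational agent is started, or at "hormonal therapy affecting the hypothalamic-pituitary-gonadal axis or surgical intervention for endometriosis, whichever occurs first".
- **Section 7.2.1, collection period.** Adverse events and serious adverse events are collected from the first extension dose to the Follow-up visit, or to the start of another investigational agent, hormonal therapy of the same kind, or "surgical intervention for endometriosis, whichever occurs first, as also specified in the study Schedule of Activities". Once the period has closed, serious events "should be reported to the sponsor if the investigator assesses the event as related to the study drug treatment".
- **Section 5.10.3, surgery.** Surgical treatment of endometriosis is "prohibited from the Week 24/Baseline visit until the patient's final study visit unless urgently needed for patient safety".
- **Section 5.10.1 and Table 5-2, hormones.** Estrogens, progestins, GnRH analogues and hormonal contraceptives are prohibited through the Follow-up visit.
- **Section 4.5, removal from therapy.** The list of events that lead to removal includes neither endometriosis surgery nor use of a prohibited hormone.
- **Schedule of Activities, Section 6.2 and Table 7-2.** Adverse events are collected at every visit. Footnote z to the Schedule says when collection starts and gives no early stop.

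**The concern.** A treatment-emergent period should cover all the time a patient is on study drug, plus a defined tail. Closing the tail early when a new therapy begins is a reasonable choice, because later events may belong to that therapy. Closing the period while she is still dosing is different: it removes on-drug exposure, and the events that occur in it, from the summaries.

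Incidence of adverse events is a named safety endpoint. The women who meet a trigger on treatment are those who needed urgent surgery or took an additional hormone, so the time removed is not a random sample of exposure. The cut-off also falls where post-operative events, or events from combining a hormone with study drug, would be looked for. If sites also read Section 7.2.1 as an instruction to stop recording, some of those events could not be recovered at the analysis stage.

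**Working it through.** The plan gives no figure to reproduce. The check compares the definitions and then counts days.

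**1. The rule as a formula.** Let L be the date of last dose, and I, H and S the dates of another investigational agent, hormonal therapy and endometriosis surgery.

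- As written (Section 9.5): end = min(L + 30 days, I, H, S).
- Cut-offs limited to the time after dosing: end = min(L + 30 days, the first of I, H, S that falls after L).

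The two differ only when I, H or S falls on or before L.

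**2. Can a trigger precede the last dose?**

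- Surgery: yes. Section 5.10.3 allows it when urgently needed.
- Hormones: only as a deviation, since they are prohibited. A safety definition still has to work when deviations occur.
- Does dosing then stop? No listed rule says so. The nearest item in Section 4.5 is gross noncompliance, a judgement whose examples concern study drug, visits and eDiary completion.

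**3. Time excluded.** The inputs are 28 weeks of open-label treatment (28 × 7 = 196 days, Section 4.1) and the 30-day tail (Section 9.5). Assume a trigger on extension day d, with dosing continued to day 196. As written, the period ends on day d. With the cut-offs limited to the time after dosing, it ends on day 196 + 30 = 226.

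- Total excluded = 226 − d days
- On-drug part = 196 − d days

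| Trigger on extension day d | Total days excluded | Of which on drug |
|---|---|---|
| 28 | 198 | 168 |
| 42 (Week 30) | 184 | 154 |
| 98 | 128 | 98 |
| 168 | 58 | 28 |

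**4. As a share of the period.** The treatment-emergent period starts at the first randomized dose in the parent study, so the base is 52 weeks. For a Week 30 trigger, 52 − 30 = 22 weeks are lost, and 22/52 = 42% of on-treatment time. With the tail, the excluded time is 184 of 364 + 30 = 394 days, or 47%.

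**5. The collection rule beside the other passages.**

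| Passage | Does recording stop at a trigger? |
|---|---|
| Section 7.2.1 | Yes, except serious events judged related |
| Schedule of Activities and footnote z | No cut-off given; every visit through Follow-up |
| Section 6.2 | No cut-off given; each visit |
| Table 7-2 | No cut-off given; each visit |

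Section 7.2.1 says its limits also stand in the Schedule of Activities. The trigger cut-offs do not appear there.

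**The case against.** The strongest reply is that the clause was meant to apply after dosing. Section 6.3 uses nearly the same list of triggers to bring forward the Follow-up visit, which is itself timed from the last dose, and Section 7.2.1 attaches the list to that visit. A strictly literal reading also produces an oddity: unless the word for another carries over to the second item, relugolix is itself a hormonal therapy acting on that axis. This is a fair account of the likely intent. But neither Section 7.2.1 nor Section 9.5 states it, and both will be applied by people working from the text.

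The setting is also narrow. Entry criteria exclude women who expect or want endometriosis surgery, hormones are prohibited, and Section 4.5 lets the investigator or medical monitor remove a patient for safety or poor compliance. This stands as a limit on how many women are affected. It does not establish that dosing stops at the trigger.

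A reader might infer that no later event in such a woman would be collected. The documents do not support that. Related serious events remain reportable, ALT or AST elevations of at least 3 × ULN are reported throughout open-label treatment (Section 7.5), and the Schedule, Section 6.2 and Table 7-2 keep recording going at each visit. Loss of collection is a conflict between sections, not a certainty.

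A reader might also put the Week 30 loss at 22 of 28 weeks (79%). That is the open-label segment only; the treatment-emergent period begins in the parent study.

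Finally, Section 4.6 allows hormonal contraception from 4 weeks after the last dose, which might seem to cut the 30-day tail to 28 days. That applies only if menses have returned and concerns two days off drug, where an early cut-off is defensible. It adds nothing to this point.

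**Conclusion.** The point holds for the text of Amendment 1. Under Section 9.5 as written, on-drug events after a trigger are not counted as treatment-emergent. Under Section 7.2.1, sites have conflicting instructions on whether to keep recording them.

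For one woman the size can be large: 22 of 52 on-treatment weeks plus 30 days for a Week 30 trigger, assuming she doses to Week 52. For the trial it cannot be computed, because the documents give no rate of on-treatment surgery or hormone use. It is probably small. Lost weeks also do not translate directly into lost incidence, since Section 9.5 counts a repeated event once per patient. The case for changing the rule is that the loss is selective and the repair is simple.

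The conclusion rests on the literal wording and on continued dosing after a trigger, which the protocol permits but does not require. Amendments 2, 3 and 3.1 are listed, but their Sections 7.2.1 and 9.5 are not in the part available, so whether the clause is still in force is unknown. The Amendment 2 contents page shows open-label treatment running to Week 104. If the clause was carried over unchanged, the same trigger would exclude more on-drug time.

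**What to change.** - In Sections 7.2.1 and 9.5, state that the investigational-agent, hormonal-therapy and surgery cut-offs apply only when they fall after the last dose of study drug.
- Count every event that starts while the woman is on study drug as treatment-emergent, and flag those that start after a trigger so they can be shown with and without.
- Reconcile Section 7.2.1 with the Schedule of Activities (including footnote z), Section 6.2 and Table 7-2, so that sites have one instruction on how long to record events.
- Check whether the later amendments keep the wording, and correct it there if they do.

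The cost is one clause in each of two sections, a flag in the analysis data and a consistency edit. The downside is small: some on-drug events will be confounded by the added therapy or surgery, which the flag makes visible. The change concerns only the collection and analysis window; it does not touch dosing, the prohibitions or the removal rules.
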